9.4.2 ANALYSIS OF THE PRIMARY ENDPOINT(S)

The primary outcome, change in inflammatory biomarker (CRP, IL-6, TNF- α), will be measured using a series of blood draws as described in **Section 6.1**. For our primary analysis, we are interested in the change over the course of the first 3 months, during which group 1 completes the exercise program and group 2 acts as a control. The change in inflammatory biomarker will be calculated by measuring the difference between the first and second measurement for each participant. We will then present the mean change by group with corresponding standard deviations. Analysis of covariance (ANCOVA) will be used to compare the change in each of the 3 inflammatory biomarkers between groups: An unadjusted model will account for a participant's baseline biomarker measurement while an adjusted model will include the set of covariates identified in **Section 9.4.6**. If these analyses identify a significant difference in change of inflammatory biomarkers associated with participation in the exercise program, next steps will assess if this change is still present three months after completing the exercise program. Using data from both groups in aggregate, paired t-tests will be used to compare the inflammatory marker level directly after participation in the exercise program and inflammatory marker levels three months afterward.

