While exercise has been shown to reduce biomarkers of inflammation^{6,7} and increase the release of anti-inflammatory proteins⁷ in healthy individuals, it has not been extensively examined in individuals with SCI. In one study, CRP, IL-6, and TNF- α were all reduced in individuals with SCI after participation in a 10 week cycling exercise program.⁸ In another study, CRP and erythrocyte sedimentation rate (ESR; test to detect inflammation) were both reduced in individuals with SCI following a 6-week body weight supported treadmill training program.⁹ However, these studies included small sample sizes (18 and 14, respectively), did not include a control group, examined biomarkers immediately after the program, and included only cardiovascular exercise. In another study that included both individuals with SCI and multiple sclerosis (MS), there was a significant decrease in TNF- α after one exercise session.¹⁰ However, these results included both patients with SCI and MS and only a single exercise session. Thus, the generalization of the results, the long-term effects, and the effects of strength training are not yet known.

While there is limited evidence that an exercise program can reduce inflammation in individuals with SCI, exercise has been shown to have other important beneficial effects. A recent review found evidence that exercise can improve fitness (cardiorespiratory fitness, power output, muscle strength) and cardiometabolic health (body composition, cardiovascular risk) of individuals with SCI.¹¹ Another review reported evidence that exercise can greatly improve the physical and psychosocial well-being of individuals with SCI.¹² As the result, if the barriers to exercise participation after a SCI can be overcome, individuals may have multiple positive health benefits. For this study, we anticipate that a 12-week adaptive exercise program will reduce chronic inflammation and improve overall health in individuals with SCI.

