4 STUDY DESIGN

4.1 OVERALL DESIGN

Study Design:

This study is an unblinded, randomized, 2-arm clinical trial.

Hypotheses:

Primary Hypothesis: We hypothesize that exercise will reduce inflammatory biomarkers.

Secondary Hypothesis: We hypothesize that exercise will improve strength and cardiovascular health.

Tertiary Hypothesis: We hypothesize that exercise will improve QOL.

Randomization:

At the consent visit, participants will be randomized into one of two treatment groups. Randomization is explained in **Section 6.3**.

Treatment Groups:

Group 1: 10 participants will begin the exercise program immediately (3x per week for 12 weeks = 36 total).

Group 2: After a 12-week delay, 10 participants will begin the exercise program (3x per week for 12 weeks = 36 total).

Study Intervention:

Exercise sessions will last approximately 1 hour and will be lead by exercise physiologists and therapists. Additional details are discussed in **Section 6.1**.

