9.4.3 ANALYSIS OF THE SECONDARY ENDPOINT(S)

Similarly structured ANCOVA models will be used to evaluate the change in secondary outcome measures (HR, RPE, and maximal weight) associated with participation in the intervention. Data from the first 3 months from both groups will be compared in both unadjusted and adjusted analyses. This maintains the

benefits of including control data when estimating the intervention effect on strength and cardiovascular health. If there is a significant change in secondary outcome measures after participation in the intervention, participants' measurements directly post-exercise program will be compared to those taken 12-weeks later to determine if the effect persists. These measurements will be compared using paired t-test or Wilcoxon signed rank tests, as appropriate, with no group comparisons.

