9.4.4 ANALYSIS OF THE TERTIARY ENDPOINT(S)

To evaluate the effect of the exercise program on QOL, SCI-QOL scores will be analyzed similarly to the primary and secondary endpoints. This includes exploration of any observed effects on QOL in the 12-weeks after program completion.

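### The three-month persistence test is an uncontrolled before-after comparison, and the between-arm contrast that the design already yields at about week 24 is never used

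*Combined protocol and SAP*

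**What the plan says.** Section 9.4.2 confines the controlled analysis to the first three months, when "group 1 completes the exercise program and group 2 acts as a control". If that analysis is significant, "next steps will assess if this change is still present three months after completing the exercise program". The method is: "Using data from both groups in aggregate, paired t-tests will be used to compare the inflammatory marker level directly after participation", set against the level three months later.

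Section 9.4.3 does the same for heart rate, perceived exertion and maximal weight: "These measurements will be compared using paired t-test or Wilcoxon signed rank tests, as appropriate, with no group comparisons". Section 9.4.4 carries the approach to quality of life: "SCI-QOL scores will be analyzed similarly to the primary and secondary endpoints". The between-group tests in section 9.4.10 are for exploratory outcomes such as adherence. No section compares the randomised arms on an efficacy outcome after the first three months.

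On the design, section 4.1 has Group 1 start at once and states: "Group 2: After a 12-week delay, 10 participants will begin the exercise program". Section 6.1.2 gives three blood draws for Group 1 and four for Group 2.

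**The concern.** A pooled before-after test cannot separate the effect of stopping exercise from anything else that moves the measurements over the same 12 weeks. The protocol recognises such influences: section 8.1 tracks injury, illness and life events because they may affect the biomarkers. Upward movement in both arms would look like a fading effect, and downward movement would hide real fading.

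The staggered start provides a check at no cost in visits or blood. When Group 1 reaches its second post-treatment draw, Group 2 should be at its first, and a comparison of the arms at that time removes any change common to both. Section 9.4.1 treats any analysis not listed in the plan as after the fact, so the contrast carries little weight unless it is written in beforehand.

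**Working it through.** **Timing (derived, not stated).** Inputs: 12-week delay and 12-week programme (section 4.1), follow-up three months after the programme (section 9.4.2; 12 weeks in 9.4.3), three and four draws (section 6.1.2).

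| | about week 0 | 12 | 24 | 36 |
|---|---|---|---|---|
| Group 1 | Pre-treatment 1 | Post-treatment 1 | Post-treatment 2 | – |
| Group 2 | Pre-treatment 1 | Pre-treatment 2 | Post-treatment 1 | Post-treatment 2 |

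This agrees with the 6 to 9 months of participation in the synopsis.

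**The plan's own figure.** Section 9.2 states 80% power for 1.3 SD with 10 per arm at 5%. For a two-sided two-sample t-test with 18 df, the noncentrality is 1.3 × √(10/2) = 2.91 and power is 78.5%. Exactly 80% needs 1.325 SD, which rounds to 1.3, so the figure reproduces.

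**Assumptions.** The documents give no within-person correlation ρ and no drift. I take unit SD at each visit, equal correlation between all visits (0.5, range 0 to 0.7), and a common drift d per 12 weeks. At ρ = 0.5 the SD of a change is √(2 × 0.5) = 1, so level and change share one scale. The gate on a significant first-stage result is not modelled.

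**What each analysis estimates.** Let e be the immediate effect and w the amount lost in the 12 weeks after stopping.
- Paired, Group 1: (e + w + 2d) − (e + d) = w + d.
- Paired, Group 2: (e + w + 3d) − (e + 2d) = w + d.
- Week 24, Group 1 minus Group 2: (e + w + 2d) − (e + 2d) = w.

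**Precision at ρ = 0.5.**
- Paired, n = 20: SE = √(2(1 − ρ)/20) = √0.05 = 0.22 SD.
- Week-24 ANCOVA on baseline, 10 per arm: SE ≈ √((1 − ρ²) × 2/10) = √0.15 = 0.39 SD; about 0.40 in simulation.

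**No true loss (w = 0).** Chance that the paired test is significant, from the noncentral t with 19 df and noncentrality d/√(2(1 − ρ)/20):

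| Drift per 12 weeks | ρ = 0.3 | ρ = 0.5 | ρ = 0.7 |
|---|---|---|---|
| 0.2 SD | 11% | 13% | 19% |
| 0.3 SD | 19% | 25% | 38% |
| 0.5 SD | 43% | 56% | 78% |

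Simulation at ρ = 0.5 gives about 14%, 25% and 56%. With upward drift, almost all of these are false losses. The week-24 ANCOVA stays at 5%.

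**Half the effect lost (w = 0.65), drift −0.5 SD, ρ = 0.5.** The paired test estimates 0.65 − 0.5 = 0.15 SD and is significant in about 10% of trials. The week-24 ANCOVA estimates about 0.65 SD and is significant in about 34%.

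**No drift.** For a 0.65 SD loss, power is about 34% for the ANCOVA (28% to 48% for ρ from 0 to 0.7) against 79% for the paired test at ρ = 0.5. For complete loss of 1.3 SD, the ANCOVA has about 87% (76% at ρ = 0, 96% at ρ = 0.7). The loss detectable with 80% power, by noncentral t, is:

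| ρ | 0 | 0.3 | 0.5 | 0.7 |
|---|---|---|---|---|
| Week-24 ANCOVA | 1.33 SD | 1.27 | 1.15 | 0.95 |
| Paired test | 0.93 SD | 0.78 | 0.66 | 0.51 |

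**Break-even.** The paired estimate has the smaller mean squared error while d² + 0.05 < 0.15, that is, while |d| < √0.10 = 0.32 SD. Across ρ from 0 to 0.7 the threshold is 0.27 to 0.33 SD.

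**The case against.** The case against acting has several parts.

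- **Precision.** The paired test is far more precise. If the conclusion rested on the week-24 contrast alone, a half-lost effect would be non-significant in about two trials of three and could be mistaken for persistence. This stands, and it decides the form of the fix.
- **The drift is assumed.** At 0.2 or 0.3 SD and ρ = 0.5, the paired estimate still has the smaller total error. Section 9.2 implies rolling enrolment: 10% of 25 per month is 2.5 per month, so 25 people take about 10 months. With even entry over that time and a yearly sine wave (both assumed), season would need an amplitude of about 1.6 SD to shift the pooled estimate by 0.3 SD. Section 6.1.2 stores the IL-6 and TNF-α samples frozen and does not state the run order, so assay drift is possible but not shown. Practice effects are not plausible for serum markers. All of this lowers the likely size of the bias. It does not supply a control.
- **The contrast is not a clean one.** A reader might infer that at week 24 the arms differ only in time since exercise. The documents do not support that. Section 7.2 allows replacement of people randomised but untreated, section 10.4 records that enrolment was raised for this reason, section 9.4.1 drops incomplete cases, and Group 2 has 12 extra weeks in which to leave before starting.
- **Decay, not benefit.** No unexercised arm exists at week 24. Like the paired test, the contrast measures loss of effect, not benefit over no exercise.
- **The protocol's criticism of earlier work.** Section 2.1 says earlier studies "did not include a control group, examined biomarkers immediately after the program". A reader might infer that this trial repeats both faults. It does not: the three-month ANCOVA has a control, and later draws are taken. Only the persistence step lacks a control, and that step is conditional.

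**Conclusion.** The concern holds in a limited form. Persistence is tested only by an uncontrolled pooled comparison whose bias equals any drift common to the arms, and an available between-arm contrast free of that bias goes unused. At ρ = 0.5, drifts of 0.2 to 0.5 SD would give a false finding of change in about 14% to 56% of trials, against 5% for the week-24 ANCOVA. Correlation and drift are assumptions, the week-24 timing is derived and actual visit dates may slip, and the contrast also assumes the same immediate effect whether exercise starts at once or after the delay.

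A reader might go further and infer that the week-24 contrast should replace the paired test as the basis for the persistence statement. The documents do not support that: they give no drift figure, and whether bias or imprecision is the greater problem turns on it. The two analyses fail in different ways and belong side by side. The primary three-month comparison is not affected.

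**What to change.** In section 9.4.2, and by reference in 9.4.3 and 9.4.4:

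1. Pre-specify an ANCOVA at about week 24 of Group 1 Post-treatment 2 against Group 2 Post-treatment 1, adjusted for the Pre-treatment 1 value and analysed as randomised, reported with its estimate and 95% confidence interval.
2. Keep the paired comparison, label it uncontrolled, and report it beside the ANCOVA in the same form.
3. State the limits: the contrast estimates loss of effect, there is no unexercised arm at that time, it assumes equal immediate effects in the two arms, and replacement and complete-case exclusion weaken it.
4. Draw the persistence conclusion from both estimates and intervals, qualify it if they disagree, and do not read a non-significant result from either as persistence.
5. In section 9.4.3, delete "with no group comparisons".
6. Before extending the contrast to strength and cardiovascular outcomes, reconcile section 6.1.2, which places that testing at the first post-treatment visit, with sections 1.3 and 9.4.3, which also have it at the later one. The biomarker draws are not affected by this conflict.

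The cost is plan wording and one extra ANCOVA per outcome, with no new visits, blood or participants. The drawback is a wide interval: with SE 0.40 and 17 df, the half-width is about 2.11 × 0.40 = 0.84 SD.

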Biomarker Quantification (Aim 1): The primary outcome for Aim 1 will be change in inflammatory biomarkers: CRP, IL-6, TNF- α , as these were the primary biomarkers shown to be higher in individuals with SCI compared to healthy individuals in previous studies. Patients in Group 1 will undergo 3 blood draws and patients in Group 2 will undergo 4 blood draws. Patients will give approximately 2.5 teaspoons of blood for each blood draw. Blood samples will be collected by the HealthPartners Neuroscience Center laboratory staff. CRP will be analyzed through Regions Hospital Central Laboratory. IL-6 and TNF- α will be analyzed using the MAGPIX® by Millipore Sigma™, a multiplex ELISA, allowing the quantification of multiple analytes from a single sample by combining magnetic and fluorescent technology. After collection, blood will be allowed to clot for at least 30 minutes before centrifuging for 10 minutes at 1000xg. Serum will be removed, aliquoted and stored in sterile cryo-preservation tubes in -80°C freezers onsite in a secured location with temperature tracking until time of analysis. At the time of analysis samples will be thawed and diluted 1:2 in Assay Buffer provided by a custom Milliplex® kit: HCTYA-60K-03 (IL6, TNFa, IL1RA). The beads provided by the kit will also be added and the plate will be incubated on a plate shaker following the kit protocol. After incubation the plate will be placed on a magnet and washed, then incubated with a secondary antibody provided by the kit. Once the secondary incubation is completed the plate will be again placed on a magnet and washed before being run by the MAGPIX®. Data quantification will be acquired using the xPonent® software provided by Millipore Sigma™.

Strength and Cardiovascular Health (Aim 2): Participants will undergo a strength and cardiovascular test during the pre-treatment and first post-treatment visits. The strength test will consist of a 1-repetition maximum chest press test. This test quantifies the amount of weight that participants can possibly lift during the one repetition. The cardiovascular test will consist of a 6-minute submaximal exercise test using an arm ergometer following previously published methods.¹⁴ Heart rate (HR) and blood pressure will be

measured before and after the test. Rate of perceived exertion (RPE), a measure of physical activity intensity, will be measured after the test.

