9.4 STATISTICAL ANALYSES

9.4.1 GENERAL APPROACH

Discrete variables will be summarized using frequencies and percentages, while continuous variables will be summarized by means and standard deviations. If the continuous variables are found to be skewed, we will instead report medians and interquartile ranges. Statistical significance will be determined using p-values less than 0.05 and 95% confidence intervals, unless otherwise indicated. All inferential tests will be two-sided. For descriptive statistics (means, SDs, proportions) where no inferential statistics were conducted, we will refrain from making confirmative statements. All covariates will be pre-specified in the sections below. Any additional analyses will be described as post-hoc and exploratory.

Distribution of the outcome variables will be assessed prior to conduct of our analyses to determine if the planned tests are appropriate and to identify outliers. If variables are found to be non-normally distributed and/or outliers are present we will explore the use of log-transformations or non-parametric tests such as the Kruskal-Wallis test.

Patients who do not complete all assessments required for a given analysis will be excluded from the model/test and described separately. If missingness > 10% within the full analytic dataset, a comparison of participants with and without missing values will be performed and used to inform possible next steps (imputation, feasibility assessment of program, etc.). Reports of injury, illness, and life events occurring during the data collection period will be summarized and compared between arms. These summaries will be used to inform possible sensitivity analysis as described in section 9.4.10. All analysis will be performed in SAS 9.4 using two-sided alphas of 0.05 to determine significance.

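### The persistence test compares post-exercise with three-month levels and never with the pre-exercise level, so it measures rebound, not whether the benefit remains

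*Combined protocol and SAP*

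**What the plan says.** Section 9.4.2 first compares the two groups over the first three months by ANCOVA, with Group 2 as the control. If that is significant, "next steps will assess if this change is still present three months after completing the exercise program". The test for this step pools both groups: "paired t-tests will be used to compare the inflammatory marker level directly after participation in the exercise program" and the level three months later.

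Section 9.4.3 does the same for heart rate, perceived exertion and maximal weight: "measurements directly post-exercise program will be compared to those taken 12-weeks later to determine if the effect persists", by paired t-test or Wilcoxon signed rank test without group comparisons. Section 9.4.4 says SCI-QOL will be handled in a similar way: "This includes exploration of any observed effects on QOL in the 12-weeks after program completion".

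The pre-exercise level enters only the month 0 to 3 comparison. The data for a comparison with it do exist: "Patients in Group 1 will undergo 3 blood draws and patients in Group 2 will undergo 4 blood draws" (section 6.1.2). By the schedule in section 1.3, Group 1 has one pre-exercise draw and Group 2 has two, and both groups have two post-exercise draws.

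**The concern.** The question and the test have different null hypotheses. The question is whether the marker is still below where it stood before exercise. The test's null is that nothing has moved since exercise ended.

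- A significant result shows some rebound. It does not show that the benefit has gone.
- A non-significant result fails to show rebound. It does not show that the benefit was kept.

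The plan sets no margin for calling the change maintained and gives no rule for reading either result. Group 2's own change over its exercise period is not tested anywhere, yet its post-exercise data are pooled into this step.

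A durability statement is likely to be reported. Section 2.1 criticizes earlier studies for measuring biomarkers immediately after the program and concludes that "the long-term effects, and the effects of strength training are not yet known". What is at stake is a wrong statement about durability.

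**Working it through.** **Inputs from the documents.** Section 9.2 gives 10 per arm, a 1.3 SD effect, 80% power and planning SDs of 2.0 (CRP), 1.0 (IL-6) and 0.5 (TNF-α). Section 9.4.1 gives two-sided alpha 0.05. It also says: "Patients who do not complete all assessments required for a given analysis will be excluded from the model/test and described separately".

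**Assumptions.** The SD of the paired difference, s, is not in the documents; I use 1.0 to 1.4 planning SD. Pooling gives n = 10 + 10 = 20 pairs. I also show n = 16, an assumed 20% loss under the complete-case rule.

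**The plan's own figure.** A two-sample t-test with 10 per arm (18 df, noncentrality d√(10/2)) has power 78.5% at d = 1.3 and 80.0% at d = 1.325. The stated 80% therefore reproduces to rounding.

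**Power of the planned persistence test.** This is a paired t-test with n − 1 df and noncentrality λ = (rebound/s)·√n. If half of a 1.3 SD effect is lost, the rebound is 0.65 SD (1.3 units of CRP). At n = 20, λ = 0.65 × 4.472 = 2.91 for s = 1.0, and 2.91/1.4 = 2.08 for s = 1.4. If a quarter is lost, the rebound is 0.325 SD.

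| True state, 1.3 SD effect | n = 20, s = 1.0 / 1.4 | n = 16, s = 1.0 / 1.4 |
|---|---|---|
| Half retained: rebound significant | 78.7% / 50.4% | 68.1% / 41.2% |
| Three-quarters retained: rebound significant | 28.2% / 16.7% | 23.0% / 14.0% |
| Nothing retained: rebound not significant | 0.02% / 2.4% | 0.2% / 6.6% |

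**Both facts in the same data.** I simulated the three visits (pre-exercise, Post-treatment 1, Post-treatment 2) with equal correlation between them, half the effect retained, n = 20 and 60,000 runs. The rebound and the remaining reduction from pre-exercise were both significant in 59% (s = 1.0) to 18% (s = 1.4) of trials. The plan would test only the rebound.

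**Smaller effects.** At a 0.5 SD effect, a complete loss goes undetected in 44% to 67% of trials (n = 20). The ANCOVA gate, approximated by the two-sample t-test, is significant in only about 19% of trials there, so this case seldom arises.

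**The replacement contrast, pre-exercise to Post-treatment 2, n = 20.**
- Half retained (0.65 SD): power 79% to 50%, equal to the rebound test by symmetry.
- Three-quarters retained (0.975 SD): power 98.5% to 84%.
- 95% CI half-width t(0.975, 19)·s/√20 = 2.093 × s/4.472, which is 0.47 to 0.66 planning SD.

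**The case against.** **Rebound is a fair way to ask the question.** The step runs only after a significant randomized comparison, so a change is already established, and how much of it reverts bears on whether it remains. A tight interval around zero rebound would support persistence indirectly. That is true, but the plan sets no such criterion. The gate also covers only Group 1's exercise period, and rebound alone does not estimate what is left relative to baseline.

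**The misreading is not written into the plan.** No section says a significant result will be called loss. The 79% to 50% is the chance of correctly detecting a real 0.65 SD rebound, and it becomes an error only if it is read as loss. This stands as a limit on the claim. However, the plan presents the test as its answer to whether the effect persists and offers no other reading.

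**A confidence interval is already planned.** Section 9.4.1 names 95% confidence intervals alongside p-values. An interval on the rebound contrast still does not estimate the remaining change from the pre-exercise level.

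**The SD range is one-sided.** It is, and the quoted ranges are not bounds. At s = 0.77 and n = 20, the half-retained rebound is significant in 95% of trials, which strengthens the main point. Complete loss at 0.5 SD is missed in 21%, which weakens the lesser one.

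**The replacement is uncontrolled and only moderately powered.** Both are correct, and the planned test is uncontrolled too. With half retained, the replacement misses the residual benefit in 21% to 50% of trials, so its interval should carry the conclusion.

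**QOL is less definite.** Section 9.4.4 fixes no follow-up test of its own; including it rests on the statement that QOL is analyzed in a similar way.

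**Conclusion.** The concern holds, and the text alone establishes it: sections 9.4.2 and 9.4.3 ask about persistence and specify a test of rebound. At the planned effect, the main risk is that a partly retained benefit is reported as lost. Missing a complete loss is rare there and becomes likely only at smaller effects. The sizes depend on the assumed paired-difference SD and, for the joint result, on equal correlation between visits.

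The weight is modest. The step is conditional and appears in no objective or hypothesis. It should be fixed because following the plan exactly would not answer the question it poses, and the remedy is cheap.

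**What to change.** In sections 9.4.2 to 9.4.4:

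1. Base the persistence statement on the within-person change, with 95% CI, from the last pre-exercise measurement (Pre-treatment 1 in Group 1, Pre-treatment 2 in Group 2) to Post-treatment 2.
2. Keep Post-treatment 1 to Post-treatment 2 as a descriptive rebound estimate with 95% CI.
3. State that a non-significant rebound is not evidence of persistence and that a significant rebound is not evidence of complete loss.
4. Report the new contrast as uncontrolled.

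**Cost.** Wording only; section 1.3 already schedules these measurements. The change should be made before analysis, because section 9.4.1 labels additional analyses post-hoc and exploratory.

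**Downside.** The new contrast spans about six months without a control, so time trends could look like retained benefit. So could test familiarity on the strength and ergometer tests, where Group 1's reference is its first test and Group 2's is its second.

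**A separate, minor point.** Section 6.1.2 says "Participants will undergo a strength and cardiovascular test during the pre-treatment and first post-treatment visits", whereas section 1.3 also schedules this testing at Post-treatment 2 and section 9.4.3 needs it there. These sections must be reconciled so that the 12-week strength and cardiovascular data exist.
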